7.3 Comparability of Patient Groups

Descriptive statistics will be used to evaluate the comparability of patients randomized to either group with respect to age, gender, cardiovascular history, functional capacity, medications and interventions administered in hospital, and course in hospital.

8. SAMPLE SIZE

8.1 Sample Size

Outcome measures for all randomized patients will be analyzed in an intention-to-treat analysis. The primary outcome of our study will be a composite of 1) death or 2) poor neurologic outcome, at 6 months. Based on our review of the literature and our own cardiac arrest database we estimate an event rate of 50% in the mild TH group. To detect a 30% relative risk reduction with 80% power and a type I error of 5% will require a sample size of 340 patients (170 per temperature group).

9. DATA QUALITY ASSURANCE

The DSMC will consist of one chairperson and two members, all external and not directly involved with the study. One member will be a qualified biostatistician/methodologist. The DSMC will review the data from the study at regular intervals and determine if it is safe to continue the study according to the protocol. The DSMC will have access to all available data from the study throughout the study duration. All Serious Adverse Events (SAEs), including deaths, will be reported immediately to the DSMC. The purpose of the DSMC will be primarily safety and no formal analysis will be done on major outcomes.

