Therapeutic hypothermia has been shown to improve neurologic outcomes and survival in comatose survivors of OHCA. Nevertheless, outcomes remain poor with as many as 60% of patients either dying or surviving with significant neurologic impairment. Despite many advances in cardiac care, these patients still suffer significant mortality and morbidity as a result of cardiac arrest. Our center has a particular interest in cardiac arrest and the use of TH to provide neuroprotection for these patients. In 2011, we established a "CODE ROSC" program in an attempt to streamline and centralize care for these patients (abstract at 2012 CCC in Toronto).

Current American Heart Association/International Liaison Committee on Resuscitation guidelines incorporate TH as the standard of care for comatose survivors of OHCA. These guidelines recommend a target temperature of 32°C-34°C to provide neuroprotection following cardiac arrest. This degree of therapeutic hypothermia is an effective therapy (compared to placebo), improving neurologic outcomes at six months in comatose survivors of out-of-hospital cardiac arrest. However, the optimal goal temperature for therapeutic hypothermia in these patients has not been investigated in large randomized trial. It is possible that a further reduction in metabolic demand that is associated with cooler temperatures may lead to a clinically significant improvement in patient outcomes.

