7.2 Efficacy Analysis

All participants, who receive study treatment, will be included in the analyses according to their initial randomization group, i.e. intention to treat analysis. No interim analysis is planned.

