10.3 Data and Safety Monitoring Committee (DSMC)

The DSMC will consist of one chairperson and two members, all external and not directly involved with the study. One member will be a qualified biostatistician/methodologist. The DSMC will review the data from the study at regular intervals and determine if it is safe to continue the study according to the protocol. The DSMC will have access to all available data from the study throughout the study duration. All Serious Adverse Events (SAEs), including deaths, will be reported immediately to the DSMC. The purpose of the DSMC will be safety.

Commented [c2]: Specify

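### The DSMC must judge whether it is safe to continue, but the plan gives it no by-arm comparison of deaths, no review schedule and no harm guideline, so an excess of deaths at 31°C could be recognised late

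*Combined protocol and SAP*

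**What the plan says.** Section 9 gives the committee its task: to look at the accumulating data periodically, at a frequency not stated, and to judge whether the trial can safely go on. It also gives it the means: "The DSMC will have access to all available data from the study throughout the study duration", and "All Serious Adverse Events (SAEs), including deaths, will be reported immediately to the DSMC". Section 12.4 sets 24 hours for reporting a death. One of the three external members is a biostatistician or methodologist.

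Section 9 then limits the work. After describing the remit as mainly one of safety, it says that "no formal analysis will be done on major outcomes". Section 7.2, under its efficacy heading, adds: "No interim analysis is planned".

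Section 10.3 repeats the duty to "determine if it is safe to continue the study according to the protocol" but omits the sentence about formal analysis. It gives the committee's purpose simply as safety, and an unresolved drafting comment, 'Specify', follows.

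Death is one half of the primary composite (sections 5.1 and 8.1) and the first secondary outcome (section 5.2). On the temperature range, section 4.1 says: "These guidelines recommend a target temperature of 32°C-34°C". The test arm aims for 31°C.

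**The concern.** The committee has a decision to make, but the plan does not describe the comparison on which that decision would rest. No section says how often or after how many patients it meets, whether it sees data by arm, whether deaths are tabulated by arm, or what difference should prompt concern. The only analysis described elsewhere is a blinded one by the trial statistician (section 10.2).

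This matters more here than in a trial with few deaths. The anticipated rate of the composite is 50% at 34°C, so death reports are likely to be frequent in both arms. A run of individual reports does not show an imbalance; a table by arm does. The test temperature also lies below the guideline range that the protocol cites, and section 4.3 foresees that cooling may contribute to intractable arrhythmia or refractory hypotension. An excess of deaths is therefore a possibility worth planning for. At stake is the number of patients enrolled before such an excess is seen.

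**Working it through.** **The plan's own figure.** Inputs from sections 3.6.1 and 8.1: 50% v 35%, alpha 0.05, power 80%, 1:1 allocation. With the pooled two-sided formula and no continuity correction, the mean rate is 0.425 and

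n per arm = [1.96 × √(2 × 0.425 × 0.575) + 0.8416 × √(0.50 × 0.50 + 0.35 × 0.65)]² / 0.15²
= [1.96 × 0.6991 + 0.8416 × 0.6910]² / 0.0225
= 1.9518² / 0.0225 = 169.3, so 170 per arm and 340 in total.

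This matches the plan. The plan does not state sidedness, but the two-sided test reproduces its number (one-sided gives 268).

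**What an excess would mean.** At full enrolment, 170 patients are treated at 31°C. An excess of 10, 15 or 20 percentage points is 170 × 0.10 = 17, 170 × 0.15 = 25.5 or 170 × 0.20 = 34 additional deaths.

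**What a simple harm guideline would detect.** The documents give no mortality rate, look times or boundary, so all of these are assumptions:
- Control mortality (34°C) of 40%.
- Looks at 25%, 50% and 75% of enrolment, that is 85, 170 and 255 patients, or about 43, 85 and 128 per arm.
- At each look, z = (p₃₁ − p₃₄) / √[p̄(1 − p̄) × 2/n], where p̄ is the pooled proportion. The guideline is crossed if z ≥ 2.576 (one-sided p<0.005).
- Deaths are known at each look, and every crossing stops the trial.

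Two examples at the middle look (85 per arm, 34 deaths at 34°C, since 0.40 × 85 = 34):
- 51 deaths at 31°C (60%): p̄ = 85/170 = 0.50, and z = 0.200 / √(0.25 × 2/85) = 0.200 / 0.0767 = 2.61. The guideline is crossed.
- 47 deaths at 31°C (about 55%): p̄ = 81/170 = 0.476, and z = 0.153 / 0.0766 = 2.00. It is not crossed.

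Simulated chance of crossing at any of the three looks:

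| Deaths, 34°C v 31°C | Excess (points) | Crossed |
|---|---|---|
| 40% v 40% | 0 | 1.2% |
| 40% v 45% | 5 | 6% |
| 40% v 50% | 10 | 21% |
| 40% v 55% | 15 | 49% |
| 40% v 60% | 20 | 77% |

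Mean enrolment falls from 170 to about 130 per arm in the fourth row and about 102 in the fifth. The assumed control rate matters little: a 15-point excess is flagged in 51% of trials at 30% v 45% and in 49% at 50% v 65%.

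**Other boundaries.** With two looks, at one third and two thirds of enrolment, and 40% v 55%:

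| Boundary | Crossed at 40% v 55% | Crossed with no difference |
|---|---|---|
| z ≥ 3 | 25% | 0.25% |
| one-sided 0.01 | 50% | 1.7% |
| one-sided 0.025 | 66% | 4.1% |

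The choice trades sensitivity against false alarms, and no single boundary is the right one.

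**The case against.** The strongest objection is that the plan may not exclude a comparison of deaths at all. The term for the outcomes left unanalysed is undefined. It shares a sentence with a statement that the committee is primarily about safety, and the ban on interim analysis sits under an efficacy heading. Section 10.3 leaves the sentence out. The intent could be only that there will be no interim efficacy test, which would be sound and would protect the 5% level. This stands as far as it goes: a reader might infer that the plan bars the DSMC from comparing deaths, and the documents do not clearly say so. But the wording includes death on its natural reading, and even on the narrower reading nothing supplies the missing comparison.

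Second, the safeguards are real. The committee is external, has a biostatistician, sees all data, hears of each death within 24 hours and could tabulate deaths and advise stopping on judgement. A reader might infer that an excess of deaths would run unseen to full enrolment. The documents do not support that; they support only that it could be recognised late. Nor do they describe a committee reading unadjusted p-values at each review, so a chance stop by that route is also conjecture.

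Third, the illustration favours the rule. It treats the present committee as never acting, every crossing as a stop although the guideline is non-binding, and follow-up as instantaneous. All three points stand. Excesses of 5 or 10 points are mostly missed, and about half of trials with a 15-point excess would still enrol fully.

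Last, leaving safety to expert judgement is a legitimate choice. That is true, but the committee needs a table by arm to exercise it, and the open 'Specify' comment suggests that the remit was not finished.

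**Conclusion.** The concern holds as a gap in the safety monitoring plan. The DSMC must decide whether continuation is safe, while section 9 appears to withhold formal analysis of outcomes that naturally include death, and no section provides a by-arm comparison, a schedule or a guideline for harm. The absence of an interim efficacy analysis is not a fault.

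On the stated assumptions, a modest guideline would flag about half of trials with a 15-point excess and about three quarters with a 20-point excess, at a false-signal rate near 1%. It does little for excesses of 10 points or fewer. These figures rest on an assumed mortality rate, complete death data at each look and stopping at every crossing, so they are an upper guide to the benefit. This is a worthwhile, inexpensive improvement; it does not show that the trial as written is unsafe.

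**What to change.** Replace the limiting sentence in section 9 with wording such as:

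> No interim efficacy analysis will be done. At 25%, 50% and 75% of enrolment the DSMC biostatistician, holding the allocation codes in confidence, compares all-cause deaths by arm (30-day death among patients with 30 days of follow-up, plus all deaths to date), for harm only, with a non-binding guideline such as one-sided p<0.005. The final two-sided 5% level is unchanged.

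The look times and threshold are examples; what matters is that they are set in advance. State which of the two death comparisons carries the guideline, because the 1.2% false-signal rate is for a single comparison. Make sections 7.2 and 10.3 agree with section 9, and resolve the 'Specify' comment in 10.3. The trial statistician stays blinded, as section 10.2 provides.

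Cost: a few sentences, a secure route for the codes to the DSMC biostatistician, and three short closed tables from a member already on the committee. Because there is no stop for benefit, no efficacy alpha is spent and the sample size stays at 340. The downside is about a 1% chance of a false harm signal, which the committee may override.

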10. STUDY COMMITTEES

10.1 Steering Committee

The steering committee, chaired by the principal investigator, will have the responsibility of overseeing the scientific conduct of the study. Members are listed in Appendix 3.

10.2 Clinical Event Adjudication Committee

The adjudication committee will consist of a chairperson and two members. Members will not be investigators or co-investigators. The committee will adjudicate the following events on a regular basis: 1) death, 2) 6 month neurological outcome results according to the DRS, 3) stroke, and 4) stent thrombosis. Members will be provided with relevant physician and nurses' notes, ECGs and laboratory test results. The research

coordinator will mask the treatment group before providing documentation. The adjudication committee will perform the verification of clinical outcomes in a blinded manner and the statistician will perform a blinded analysis.

10.3 Data and Safety Monitoring Committee (DSMC)

The DSMC will consist of one chairperson and two members, all external and not directly involved with the study. One member will be a qualified biostatistician/methodologist. The DSMC will review the data from the study at regular intervals and determine if it is safe to continue the study according to the protocol. The DSMC will have access to all available data from the study throughout the study duration. All Serious Adverse Events (SAEs), including deaths, will be reported immediately to the DSMC. The purpose of the DSMC will be safety.

Commented [c2]: Specify

11. ANALYSIS OF DATA

Statistical analysis will be performed under the supervision of [name] in the Methods Center at the University of Ottawa Heart Institute.

12. ASSESSMENT AND REPORTING OF ADVERSE EVENTS

12.1 Definition of an Adverse Event (AE)

An adverse event is any untoward medical occurrence or unfavourable and unintended sign in a subject administered a pharmaceutical product/biologic (at any dose), or medical device, whether or not considered related to the use of that product. Additionally, any event that is associated with or observed in conjunction with a product overdose (whether accidental or intentional) or a product abuse and/or withdrawal is also considered an adverse event.

12.2 Definition of Serious Adverse Events (SAE)

A serious adverse event is any adverse drug or biologic or device experience occurring at any dose that results in any of the following outcomes:

- 1) Death
- 2) life-threatening adverse event (i.e., one that places the subject, in the view of the initial reporter, at immediate risk of death from the adverse event as it occurs)
- 3) persistent or significant disability/incapacity
- 4) required in-patient hospitalization, or prolonged hospitalization
- 5) congenital anomaly or birth defect

12.3 Expedited Reporting of Serious Adverse Events

All serious adverse events, whether or not deemed drug-related or expected, must be reported by the principal investigator or designee to the Human Research Ethics Board and to the Data and Safety Monitoring Committee (DSMC) within 24 hours (one working day) of first becoming aware of the event. Serious adverse events that occur at any time after the inclusion of the subject in the study (defined as the time when the subject

signs the informed consent) up to 6 months after the subject completed or discontinued the study must be reported. The subject is considered to have completed the study either after the completion of the last visit or contact (e.g., phone contact with the investigator or designee), OR after the last dose of the study medication, whichever is later. The date of discontinuation is when a subject and/or investigator determines that the subject can no longer comply with the requirements for any further study visits or evaluations.

12.4 Reporting of Subject Death

The death of any subject during the study regardless of the cause will be reported to the Data and Safety Monitoring Committee (DSMC) within 24 hours of first becoming aware of the death.

13.1 APPENDIX 1: INVESTIGATORS

University of Ottawa Heart Institute

Principal Investigator

[name] [name]

Co-Investigators

[name]

[name]

[name]

[name].

[name].

[name]

[name]

[name] MD

[name]

[name]

[name] (Statistical Analyst)

Research Coordinator

[name], B.Sc.

13.2 **APPENDIX 2: ELIGIBILITY SCREENING FORM**

SCREENING DATE: _____

ELIGIBILITY SCREENING FORM

Before entering a subject into the study, all of the following items must be completed. If any of the items are indicated "No", the subject is not eligible for enrolment.

INCLUSION CRITERIA

	Yes	No
Out of Hospital Cardiac Arrest,	[]	[]
and		
Glasgow Coma Score \leq 8	[]	[]
and		
Return of Spontaneous Circulation	[]	[]

Before entering a subject into the study, all of the following items must be completed. If any of the items are indicated "Yes", the subject is not eligible for enrolment.

EXCLUSION CRITERIA

	YES	NO
1. Age <18 years	[]	[]
2. Pregnancy	[]	[]
3. Patients residing in a Nursing Home or patients unable to reside independently	[]	[]
4. Intracranial bleed responsible for the cardiac arrest	[]	[]
5. Severe coagulopathy with clinical evidence of major bleeding	[]	[]
6. Coma that is not attributable to cardiac arrest	[]	[]
7. Life expectancy < one year due to cause unrelated to the cardiac arrest.	[]	[]
8. Known coagulation disorder (i.e. INR >2.0, platelets <100,000 / mm3)	[]	[]
9. Participation in a study with another investigational device or drug < four weeks	[]	[]
10. The Endovascular cooling (ZOLL) device is not available	[]	[]

Will the subject participate in this trial?

Yes [] Randomization Number:
 No [] Reason:

Investigator's Signature:

Date: ___/___/___ (yr mo day)

13.4 APPENDIX 4: SAFETY AND LABORATORY TESTS

Adverse Events and Laboratory Abnormalities

Clinical Adverse Events

An Adverse Event is any untoward medical occurrence in a patient or clinical investigation subject administered a pharmaceutical product and which does not necessarily have to have a causal relationship with this treatment. An Adverse Event can therefore be any unfavourable and unintended sign (including an abnormal laboratory finding, for example), symptom, or disease temporally associated with the use of a medicinal product, whether or not considered related to the medicinal product. Pre-existing conditions that worsen during a study are to be reported as Adverse Events.

All clinical adverse events (AEs) encountered during the clinical study will be reported on the AE page of the Case Report Form (CRF). Intensity of adverse events will be graded on a four -point scale (mild, moderate, severe, life-threatening) and reported as indicated on the CRF. Relationship of the adverse event to the treatment should also be assessed.

Laboratory Test Abnormalities

Laboratory test results will be recorded on the laboratory results pages of the CRF. Laboratory test value abnormalities as such should not be reported on the AE page of the CRF as adverse events unless they result in a clinically relevant condition.

Serious Adverse Events (SAE)

Please refer to Section 12 of the Protocol.

Treatment and Follow-up of Adverse Events

Adverse events will be followed up until they have returned to baseline status or stabilized.

13.5 APPENDIX 5: ETHICAL ASPECTS

Independent Ethics Committees/Institutional Review Board

Approval from the committee will be obtained before starting the study, and will be documented in a letter to the investigator specifying the date on which the committee met and granted the approval. Any modifications made to the protocol after receipt of the Independent Ethics Committee approval will also be submitted by the investigator to the Committee in accordance with local procedures and regulatory requirements.

Investigator's Files / Retention of Documents

For each patient enrolled, a CRF must be completed and signed by the principal investigator or authorized delegate from the study staff. This also applies to records for those patients who fail to complete the study. If a patient withdraws from the study, the reason must be noted on the CRF. If a patient is withdrawn from the study because of a treatment-limiting adverse event, thorough efforts should be made to clearly document the outcome. The investigator should ensure the accuracy, completeness, legibility and timeliness of the data in the CRFs and in all required reports.

Documents will be kept for a period of 25 years after the study has been completed. This is in accordance to Health Canada. At the end of the retention period, all paper records will be disposed of in confidential waste or shredded, and all electronic records will be deleted.

Confidentiality of Trial Documents and Subject Records

Patients will be randomly assigned to treatment according to a prepared randomization schedule. The subject randomization numbers will be generated by the Investigator and will include balanced blocks for each study center. Sets of patient numbers and associated treatment(s) will be provided to the investigators in sealed opaque envelopes. The patient randomization numbers/envelopes are to be allocated sequentially in the order in which the subjects are enrolled.

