4.2.5 Blinding

The treating physician and patient will be blinded to group allocation. The only member of the health care team who is not blinded will be the treating nurse as temperature adjustments on the cooling catheter will be performed by the nurse as per protocol. Nurses will chart temperature in a separate log, as per usual. This log, however, will be kept in the patient's room and will not be a part of the medical records that the physician has routine access to. Randomization documents will be collected by nurses and or the study coordinator to ensure blinding.

Outcomes will be adjudicated by an independent, blinded committee. Cardiologists performing the follow-up assessments will be blinded. Rehabilitation physicians performing the cognitive assessments will be blinded to group allocation.

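### Appendix 5 has the Investigator generate the randomization sequence, and nothing in the supplied text keeps the list's author out of enrolment

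*Combined protocol and SAP*

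**What the plan says.** Appendix 5 (13.5, under confidentiality of trial documents) states: "The subject randomization numbers will be generated by the Investigator and will include balanced blocks for each study center". It continues: "Sets of patient numbers and associated treatment(s) will be provided to the investigators in sealed opaque envelopes". Envelopes are used one after another in order of enrolment.

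Section 4.2.4 gives the method: 1:1 allocation in blocks, sealed opaque envelopes, separate series for VT/VF and for asystole/PEA, and randomization straight after the cooling catheter is in place. It does not name who generates the sequence.

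Section 4.2.5 sets the blinding. The treating physician and the patient are blinded, and "The only member of the health care team who is not blinded will be the treating nurse". For follow-up, "Cardiologists performing the follow-up assessments will be blinded". On paperwork, "Randomization documents will be collected by nurses and or the study coordinator to ensure blinding". Section 4.3 repeats that the physician stays blind, including when asking for cooling to be abandoned.

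Section 10.2 says of the adjudication committee: "Members will not be investigators or co-investigators". It also says that "the statistician will perform a blinded analysis".

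**The concern.** An opaque envelope conceals an assignment only from people who have not seen the list. The person who wrote the sequence has seen it. Because envelopes are used in order, that person could know the next assignment in either rhythm series before deciding whether to enrol the patient at hand.

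Two things are at stake. The first is allocation concealment: if the author also enrols, the decision to enter a patient can be made with the next arm known. The second is the blinding of care and follow-up: a physician who wrote the list cannot also be a blinded treating physician or a blinded follow-up cardiologist. Decisions that the plan intends to be made blind, such as abandoning cooling, would not be blind for that person. Blinded outcome assessment limits bias in scoring. It does not undo bias in who enters the trial or in how patients are managed.

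**Working it through.** No arithmetic applies. The planned 340 patients (170 per group) play no part in this point and would not change. The check sets the relevant passages side by side.

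1. **Who makes the list?** Section 4.2.4 is silent. Appendix 5 answers: the Investigator. No other supplied text addresses it.

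2. **Who is the Investigator?** The term is not defined. In the same appendix the investigator receives the ethics approval letter, submits protocol changes and answers for the accuracy of case report forms. The eligibility screening form (Appendix 2), which records the randomization number, ends with an investigator's signature. The natural reading is a site investigator, but no individual or clinical role is identified.

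3. **Is the author kept out of enrolment?** No supplied text says so. Entry depends on a treatment plan that includes hypothermia (section 4.2.2) and on the treating physician's wish to use it (section 4.1), so there is a judgement that advance knowledge could influence.

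4. **Is the author kept out of care, follow-up and analysis?** Only indirectly. Sections 4.2.5, 4.3 and 10.2 require blinded treating physicians, follow-up cardiologists and analysis. Someone who knows the list cannot fill those roles without breaching these requirements. Appendix 5 does not carry the restriction over to the list's author.

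5. **Do the other safeguards close the gap?**
   - Sealed envelopes used in order protect against those who have not seen the list, not against its author.
   - Randomizing after catheter insertion narrows the room for selection. The author could still know the next arm before the catheter goes in.
   - Collection of randomization documents by nurses or the coordinator covers paperwork. It does not cover generation or custody of the master list.
   - Barring investigators from adjudication protects outcome classification only. It also shows that the plan states independence explicitly where it intends it. There is no matching sentence for sequence generation.

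6. **What follows?** The gap at enrolment is firm: no rule separates the author from it. For care and follow-up there is a conflict between Appendix 5 and sections 4.2.5 and 4.3, but only if the roles overlap.

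**The case against.** The strongest reply is that the plan already governs most of this. Sections 4.2.5 and 4.3 blind the treating physician without exception, 4.2.5 does the same for follow-up cardiologists, and 10.2 requires a blinded analysis. Anyone who knows the list is therefore already excluded from those roles, and since entry turns on the treating physician's wish to cool, enrolment is arguably covered too. Much of this stands: for care, follow-up and analysis the requirement exists, and what is missing is a statement of how it binds the list's author. The enrolment part does not stand. A rule that treating physicians are blinded is not a rule on who may enrol, and Appendix 5 assigns the list to an investigator while an investigator signs the form that records entry.

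A second reply is that the sentence looks like template text. It refers to blocks for each study center in a single-center trial, and it distinguishes a singular Investigator from the plural investigators who receive envelopes, which may mean that the generator is a separate party. That is a fair inference and a reason for restraint. But this is the only text on generation, and even a separate generator is not said to stay out of enrolment. The center phrase is a wording note, nothing more.

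A third reply is that harm requires the author to keep the list, consult it and act on it. Randomization after catheter insertion leaves little room for selection, and outcomes are assessed and adjudicated blind. This limits the likely damage. It does not restore concealment from the author.

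Three stronger readings should be resisted:

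- A reader might infer that an enrolling physician does know the sequence. The documents do not identify the author, so this is not shown.
- A reader might note a "Statistical Analyst" among the co-investigators in Appendix 1 and infer that this person makes the list and so defeats the blinded analysis. Nothing links that job label to generating the list.
- A reader might infer an inflated false-positive rate. No figure in the documents ties an amount of bias to this wording.

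**Conclusion.** The point holds as a shortfall in allocation concealment that is cheap to remove. Appendix 5 gives sequence generation to the Investigator and the envelopes to the investigators, and no supplied text bars the author from enrolling. If the author enrols, concealment is lost for those patients. If the author treats or follows patients, that person cannot meet the blinding of sections 4.2.5 and 4.3.

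Overlap of roles is neither shown nor excluded. The size of any bias cannot be estimated, because the documents give neither the author's identity nor the number of patients that person would handle. The case for change rests on the low cost and on making the plan's own blinding commitments hold by design.

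The conclusion assumes that Appendix 5 describes actual practice. The finding of absence covers the supplied text only, from which some pages were removed. If an independent person already generates the list, saying so settles the point.

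**What to change.** Make two phrase changes in Appendix 5:

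- In place of the phrase naming the Investigator as generator, write: *generated and held by a person with no role in enrolment, patient care, outcome assessment or the blinded analysis*.
- In place of the phrase sending the envelopes to the investigators, write: *held by the study coordinator and opened in sequence, within the rhythm series of 4.2.4, only after the patient is enrolled and the catheter is inserted*.

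The second change builds on section 4.2.5, which already has nurses or the coordinator collect randomization documents. What it adds is custody before opening and the moment of opening. As a wording note, the reference to study centers can be replaced by the two rhythm series in the same edit.

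The cost is a small amount of time from an existing independent staff member. If recruitment has begun, transfer custody of the list and record who has had access to it. Sample size, endpoint and treatment procedures do not change.
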